## 7A1 Participant Questions

**7AX.1b** \* Which of the following population-procedure study components does this document apply to? (Check all that apply)

Population	Procedure	This document applies to this population-procedure component
People Living with HIV		

**7AX.2a** \*\* Please upload the document.

[Cost effectiveness.xlsx\(0.01\)](#) | [History](#)

**7AX.3a** Please enter any comments that you wish to share with the reviewer regarding this document.

This spreadsheet will be used to collect data from APLA (on intervention costs and salaries), the intervention counselor regarding how long each session takes, and the intervention supervisor (on how long supervision takes). No participant identifying information will be included in this spreadsheet.

## 7A1 Participant Questions

ID: 2016-0940

**7A1b** \* Which of the following population-procedure study components does this document apply to? (Check all that apply)

Population	Procedure	This document applies to this population-procedure component
People Living with HIV		

**7A2a** \*\* Please upload the document.

[Pre-enrollment and baseline 10-09-2017.docx\(0.01\)](#) | [History](#)

**7A3a** Please enter any comments that you wish to share with the reviewer regarding this document.

This document combines what was previously the pre-enrollment and baseline survey questions. No questions have been changed. The documents have been combined because all questions will now be asked at the first study visit, rather than splitting the survey across the first 2 study visits. This will decrease participant burden in the second study visit (which will also include MEMS downloading, blood draws, and a possible first intervention session).

---

## 7A1 Participant Questions

**7A1b** \* Which of the following population-procedure study components does this document apply to? (Check all that apply)

Population	Procedure	This document applies to this population-procedure component
People Living with HIV		

**7A2a** \*\* Please upload the document.

[2018-11-26 Project Rise Focus Group Discussion Guidelmb.docx\(0.01\)](#) | [History](#)

**7A3a** Please enter any comments that you wish to share with the reviewer regarding this document.

Discussion Guide Questions

---

## 7A1 Participant Questions

**7A1b** \* Which of the following population-procedure study components does this document apply to? (Check all that apply)

Population	Procedure	This document applies to this population-procedure component

ID: 2016-0940

Population	Procedure	This document applies to this population-procedure component
People Living with HIV		

**TAX.2a** **\*\* Please upload the document.**[Pre-enrollment assessment 9 25 17lmb Submitted to HSPC.docx\(0.01\)](#) | [History](#)**TAX.3a** **Please enter any comments that you wish to share with the reviewer regarding this document.**

This is the pre-enrollment assessment and we have clarified its use in the consent form

---

## 7A1 Participant Questions

**TAX.1b** **\* Which of the following population-procedure study components does this document apply to? (Check all that apply)**

Population	Procedure	This document applies to this population-procedure component
People Living with HIV		

**TAX.2a** **\*\* Please upload the document.**[Participant Tracking and Locator Form 09-25-17.docx\(0.02\)](#) | [History](#)**TAX.3a** **Please enter any comments that you wish to share with the reviewer regarding this document.**

The participant tracking and location form will be used during the pre-enrollment assessment and during check-ins.

---

## 7A1 Participant Questions

**TAX.1b** **\* Which of the following population-procedure study components does this document apply to? (Check all that apply)**

Population	Procedure	This document applies to this population-procedure component
People Living with HIV		

**TAX.2a** **\*\* Please upload the document.**[Rise\\_10 13 17\\_Follow-up.docx\(0.01\)](#) | [History](#)**TAX.3a** **Please enter any comments that you wish to share with the reviewer regarding this document.**

This document is the follow-up survey. These questions were previously contained in the baseline survey and were already approved. We have simply separated out the followup questions into a new document.

---

## 7A1 Participant Questions

**TAX.1b** \* Which of the following population-procedure study components does this document apply to? (Check all that apply)

Population	Procedure	This document applies to this population-procedure component
People Living with HIV		

**TAX.2a** \*\* Please upload the document.

[COVID-19\\_Rise\\_Survey 4 28 20.docx\(0.01\)](#) | [History](#)

**TAX.3a** Please enter any comments that you wish to share with the reviewer regarding this document.

---

---

## 7A2 Recruitment Material

**TAX.1b** \* Which of the following population-procedure study components does this document apply to? (Check all that apply)

Population	Procedure	This document applies to this population-procedure component
People Living with HIV		

**TAX.2a** \*\* Please upload the document.

[Internet Recruitment Scriptrev 10 4 18.docx\(0.01\)](#) | [History](#)

**TAX.3a** Please enter any comments that you wish to share with the reviewer regarding this document.  
Revised internet recruitment script to include instructions to click on a link to be screened.

---

---

## 7A2 Recruitment Material

**7AX.1b** **\* Which of the following population-procedure study components does this document apply to? (Check all that apply)**

Population	Procedure	This document applies to this population-procedure component
People Living with HIV		

**7AX.2a** **\*\* Please upload the document.**[Rise Flyer6.pdf\(0.01\)](#) | [History](#)**7AX.3a** **Please enter any comments that you wish to share with the reviewer regarding this document.**

Revised flyer with APLA email address

---

## 7A2 Recruitment Material

**7AX.1b** **\* Which of the following population-procedure study components does this document apply to? (Check all that apply)**

Population	Procedure	This document applies to this population-procedure component
People Living with HIV		

**7AX.2a** **\*\* Please upload the document.**[Rise Card1b.pdf\(0.01\)](#) | [History](#)**7AX.3a** **Please enter any comments that you wish to share with the reviewer regarding this document.**

Updated flyer text and layout, with pictures

---

## 7A2 Recruitment Material

**TAX.1b** \* Which of the following population-procedure study components does this document apply to? (Check all that apply)

Population	Procedure	This document applies to this population-procedure component
People Living with HIV		

**TAX.2a** \*\* Please upload the document.

[Internet Recruitment Script 9-25-17.docx\(0.01\)](#) | [History](#)

**TAX.3a** Please enter any comments that you wish to share with the reviewer regarding this document.

This script will be used to recruit people using Facebook and Twitter. This script will be used to recruit people for different procedures.

---

---

## 7A2 Recruitment Material

**TAX.1b** \* Which of the following population-procedure study components does this document apply to? (Check all that apply)

Population	Procedure	This document applies to this population-procedure component
People Living with HIV		

**TAX.2a** \*\* Please upload the document.

[2018-11-19 RISE Discussion Group Flyer.docx\(0.01\)](#) | [History](#)

**TAX.3a** Please enter any comments that you wish to share with the reviewer regarding this document.

Recruitment Flyer

---

---

## 7A2 Recruitment Material

**TAX.1b** \* Which of the following population-procedure study components does this document apply to? (Check all that apply)

ID: 2016-0940

Population	Procedure	This document applies to this population-procedure component
People Living with HIV		

**TAX.2a** **\*\* Please upload the document.**[IRB Phone and in-person recruitment Script 2018-04-24 IRB Modifications KT.docx\(0.01\)](#) | [History](#)**TAX.3a** **Please enter any comments that you wish to share with the reviewer regarding this document.**

Revised recruitment script with added ineligibility criterion in track changes

---

## 7A2 Recruitment Material

**TAX.1b** **\* Which of the following population-procedure study components does this document apply to? (Check all that apply)**

Population	Procedure	This document applies to this population-procedure component
People Living with HIV		

**TAX.2a** **\*\* Please upload the document.**[Phone and in-person recruitment Script 2018-10-04 IRB Modifications.docx\(0.01\)](#) | [History](#)**TAX.3a** **Please enter any comments that you wish to share with the reviewer regarding this document.**

New screener that includes extra question for people who are recruited online (with an inclusion criterion of living in LA County or being willing to do in-person study assessments in LA County)

---

## 7A2 Recruitment Material

**TAX.1b** **\* Which of the following population-procedure study components does this document apply to? (Check all that apply)**

Population	Procedure	This document applies to this population-procedure component
People Living with HIV		

**TAX.2a** **\*\* Please upload the document.**[Phone and in-person recruitment Script 10.25.17.docx\(0.01\)](#) | [History](#)**TAX.3a** **Please enter any comments that you wish to share with the reviewer regarding this document.**

ID: 2016-0940

Revised recruitment script that specifies participants must be prescribed antiretroviral treatment (not necessarily taking it)

---

## 7A2 Recruitment Material

**7AX.1b** \* Which of the following population-procedure study components does this document apply to? (Check all that apply)

Population	Procedure	This document applies to this population-procedure component
People Living with HIV		

**7AX.2a** \*\* Please upload the document.

[COVID-19RecruitmentScript.docx\(0.01\)](#) | [History](#)

**7AX.3a** Please enter any comments that you wish to share with the reviewer regarding this document.

---

## 7A3 Data and Safety Monitoring Plan (DSMP)

**7AX.1b** \* Which of the following population-procedure study components does this document apply to? (Check all that apply)

Population	Procedure	This document applies to this population-procedure component
People Living with HIV		

**7AX.2a** \*\* Please upload the document.

[DSMPforRisetc\\_3 20 18.docx\(0.01\)](#) | [History](#)

**7AX.3a** Please enter any comments that you wish to share with the reviewer regarding this document.

Submitting a revised DSMP, base don our recent reportable event:

- Added to protocol around study staff handling of reportable events, to state that study staff will add any relevant text to participant tracking form, so that all staff are aware of any necessary protocols specific to the participant (this was suggested by our independent data and safety monitor)
- Added an additional staff member at APLA to whom incidents involving clients would be reported, who could help to further protect the client as needed (APLA's Director of HIV Access and Community-Based Services and the site PI's supervisor)
- Deleted extraneous text at the end that duplicated text in the DSP

Note that the revised DSMP was approved by the study's independent data and safety monitor.

---

## 7A5 Data Safeguarding Plan (DSP)

**7AX.1b** \* Which of the following population-procedure study components does this document apply to? (Check all that apply)

Population	Procedure	This document applies to this population-procedure component
People Living with HIV		

**7AX.2a** \*\* Please upload the document.

[DSPforRiserev6 17 20.docx\(0.01\)](#) | History

**7AX.3a** Please enter any comments that you wish to share with the reviewer regarding this document.

Revised DSP for transfer of HIV viral load photos via WhatsApp

---

## 7A6 Miscellaneous Documents

**7AX.1b** \* Which of the following population-procedure study components does this document apply to? (Check all that apply)

Population	Procedure	This document applies to this population-procedure component
People Living with HIV		

**7AX.2a** \*\* Please upload the document.

ID: 2016-0940

[QuestlettertoRAND - Sep 20, 2019.pdf\(0.01\)](#) | [History](#)

**TAX.3a** **Please enter any comments that you wish to share with the reviewer regarding this document.**  
Final letter from Quest resolving inappropriate sharing of participant data from Quest to LA County Dept of Public Health

---

## 7A6 Miscellaneous Documents

**TAX.1b** **\* Which of the following population-procedure study components does this document apply to? (Check all that apply)**

Population	Procedure	This document applies to this population-procedure component
People Living with HIV		

**TAX.2a** **\*\* Please upload the document.**

[2018-11-27 Project Rise Focus Group Recruitment and Contact Form v2 KVT.docx\(0.01\)](#) | [History](#)

**TAX.3a** **Please enter any comments that you wish to share with the reviewer regarding this document.**  
Recruitment screener

---

## 7A6 Miscellaneous Documents

**TAX.1b** **\* Which of the following population-procedure study components does this document apply to? (Check all that apply)**

Population	Procedure	This document applies to this population-procedure component
People Living with HIV		

**TAX.2a** **\*\* Please upload the document.**

[R01Rise 9 1 16\\_310pmFINAL\\_UPDATEDFORHSPC.docx\(0.01\)](#) | [History](#)

**TAX.3a** **Please enter any comments that you wish to share with the reviewer regarding this document.**  
This is the NIH R01 proposal

---

ID: 2016-0940

## 7A6 Miscellaneous Documents

**TAX.1b** \* Which of the following population-procedure study components does this document apply to? (Check all that apply)

Population	Procedure	This document applies to this population-procedure component
People Living with HIV		

**TAX.2a** \*\* Please upload the document.

[HIPPA Form 09-25-17 edited 2019-05-10 kvt.docx\(0.01\)](#) | [History](#)

**TAX.3a** Please enter any comments that you wish to share with the reviewer regarding this document.

Revised HIPAA form - only change is that APLA is not called "APLA Health & Wellness"

## 7A6 Miscellaneous Documents

**TAX.1b** \* Which of the following population-procedure study components does this document apply to? (Check all that apply)

Population	Procedure	This document applies to this population-procedure component
People Living with HIV		

**TAX.2a** \*\* Please upload the document.

[CMH\\_FWA letter exp 01-2019 RM.pdf\(0.01\)](#) | [History](#)

**TAX.3a** Please enter any comments that you wish to share with the reviewer regarding this document.

Children's Mercy Hospital's (CMH) FWA letter; CMH will defer to the RAND HSPC for Co-I [name]. Co-I [name] will train the intervention counselor; as part of the training, she may be sent recordings of counseling sessions of participants through a secure SharePoint site. This will allow her to provide guidance about specific issues that may arise on which the team would like her input.

## 7A6 Miscellaneous Documents

**TAX.1b** \* Which of the following population-procedure study components does this document apply to? (Check all that apply)

Population	Procedure	This document applies to this population-procedure component
People Living with HIV		

ID: 2016-0940

Population	Procedure	This document applies to this population-procedure component
<hr/>		

People Living with HIV

**TAX.2a** **\*\* Please upload the document.**[CMH\\_Request to Rely on External IRB has been Approved 2:14:17.pdf\(0.03\)](#) | [History](#)**TAX.3a** **Please enter any comments that you wish to share with the reviewer regarding this document.**

Children's Mercy Hospital IRB approval of reliance agreement

---

## 7A6 Miscellaneous Documents

**TAX.1b** **\* Which of the following population-procedure study components does this document apply to? (Check all that apply)**

Population	Procedure	This document applies to this population-procedure component
<hr/>		

People Living with HIV

**TAX.2a** **\*\* Please upload the document.**[Patient Instructions for use of cap 09-25-17.doc\(0.02\)](#) | [History](#)**TAX.3a** **Please enter any comments that you wish to share with the reviewer regarding this document.**

Signed APLA reliance agreement

We have also included the patient instructions for use of CAP

---

## 7A6 Miscellaneous Documents

**7AX.1b** \* Which of the following population-procedure study components does this document apply to? (Check all that apply)

Population	Procedure	This document applies to this population-procedure component
People Living with HIV		

**7AX.2a** \*\* Please upload the document.

[CheckinvisitsandRandomizationform10-16-17.docx\(0.01\)](#) | [History](#)

**7AX.3a** Please enter any comments that you wish to share with the reviewer regarding this document.

Document for checking in with participants about updating contact information, downloading electronic adherence data, and randomizing (1-month session only)

Replaces check-in and use of MEMS form combined (which was similar but did not include the randomization for the first check-in)

---

---

## 7A6 Miscellaneous Documents

**7AX.1b** \* Which of the following population-procedure study components does this document apply to? (Check all that apply)

Population	Procedure	This document applies to this population-procedure component
People Living with HIV		

**7AX.2a** \*\* Please upload the document.

[HIPPA Form 09-25-17.docx\(0.01\)](#) | [History](#)

**7AX.3a** Please enter any comments that you wish to share with the reviewer regarding this document.

This HIPPA form authorizes the release of medical information. It is also a consent form, but we already have another consent form, so we are uploading the HIPPA in miscellaneous documents instead.

---

ID: 2016-0940

## 7A6 Miscellaneous Documents

**7AX.1b** \* Which of the following population-procedure study components does this document apply to? (Check all that apply)

Population	Procedure	This document applies to this population-procedure component
People Living with HIV		

**7AX.2a** \*\* Please upload the document.

[Project Rise Retention LetterOct2020.docx\(0.01\)](#) | [History](#)

**7AX.3a** Please enter any comments that you wish to share with the reviewer regarding this document.

We have approval to send a letter to participants' home (if they consent to being contacted via mail). This is a draft of the letter that we will send.

## 7A6 Miscellaneous Documents

**7AX.1b** \* Which of the following population-procedure study components does this document apply to? (Check all that apply)

Population	Procedure	This document applies to this population-procedure component
People Living with HIV		

**7AX.2a** \*\* Please upload the document.

[Rise2.0InterventionManual 9 26 17.docx\(0.02\)](#) | [History](#)

**7AX.3a** Please enter any comments that you wish to share with the reviewer regarding this document.

APLA's FWA letter; APLA will defer to the RAND HSPC.

We are also including the intervention manual.

## 7A6 Miscellaneous Documents

**7AX.1b** \* Which of the following population-procedure study components does this document apply to? (Check all that apply)

Population	Procedure	This document applies to this population-procedure component
People Living with HIV		

ID: 2016-0940

**7A.X.2a** **\*\* Please upload the document.**[Project Rise Consent Form edited 2019-05-10.docx\(0.01\)](#) | [History](#)**7A.X.3a** **Please enter any comments that you wish to share with the reviewer regarding this document.**

Revised consent form - only change is that APLA is not called "APLA Health & Wellness"

ID: 2016-0940

## 8A Conclusion

### 8A1 Other Ethical Issues

**8A1.1** **\* Does the proposed study involve any ethical issues not already discussed in the study application?**

no

**8A2** **Please enter any other comments or information that you would like to share with the HSPC reviewer that would be relevant to the review.**

This study was funded on May 1, 2017. All study documents have now been uploaded (post-JIT review).

Note that this study is very closely related to 2011-0744-CR05, with similar procedures, setting, and study team.

Version 2.10

Clinicaltrials.gov Cover Sheet

Official Title: A Randomized Controlled Trial of an Antiretroviral Treatment Adherence Intervention for HIV+ African Americans

NCT03331978

Date: 10.30.2017

Statistical Analysis Plan

Descriptive statistics will be performed on all study variables. If related to the primary study variables, analyses will treat covariates as confounding variables. If we have high retention and find statistically significant differences between respondents and non-respondents at follow-up, we will construct and employ inverse predicted probability nonresponse weights. If item non-response is substantial, we will address it through multiple imputations. We may transform outcomes with skewed distributions (log or other as appropriate) to stabilize error variances and reduce the influence of outliers in regression models.

To assess Rise's effects on adherence and viral load, we will use generalized linear mixed models. Specifically, we will employ a repeated-measures logistic regression approach to predict optimal adherence (i.e., dichotomous adherence) with electronic monitoring data collected at enrollment and each follow-up. We will use as covariates any socio-demographic, psychosocial, and contextual variables that are associated with the adherence outcome. We assume a linear trend over time for adherence. We can also explore non-linear time trends for sensitivity analysis to this specification or assumption. To assess Rise's effects on viral suppression, we will conduct similar logistic regressions predicting viral load (dichotomized as undetectable vs. detectable) at 6- and 12-months post-enrollment. We will use similar repeated-measures linear models to examine Rise's effects on linear adherence (percentage of prescribed doses taken).

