### 5A2.4 \* If "B", please describe how individuals will be selected into the intervention/treatment and control groups (e.g., random assignment of individuals/groups or quasi-experimental designs comparing existing groups). If already described above in 5A1, please indicate that below.

A blocked 1:1 randomization design with stratification by viral suppression (with randomly alternating blocks of 2, 4, and 6 to prevent anticipation of condition) will help to ensure balance across arms. The statistician will use a random numbers generator to devise a randomization log and a set of numbered randomization envelopes. In the log, treatment assignment specifications will be left blank to prevent condition foreknowledge. After the project director records each ID in the log (immediately after the baseline survey, using results from pre-baseline confirmation of viral load via medical records for stratification), s/he will open the corresponding randomization envelope.

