## 5D Procedures - Secondary Data

---

5D1 \* Which previously collected person-level information (e.g., medical records, census data, employment records, education records, other existing datasets) will you acquire? If unsure, please list what you are considering.

Participants will provide consent for paper and electronic medical record data extraction from their usual HIV clinic. During screening, we will obtain permission to extract the two most recent viral loads from medical records, for use in stratification by viral suppression for the randomization process. After the 12-month follow-up, we will extract past 2-year viral load, CD4 counts, ART prescriptions, clinic visits, and associated dates. We have successfully used multiple methods to obtain such data from multiple different clinics across Los Angeles County (e.g., confidential faxes, multiple calls, in-person clinic visits, asking participants to bring lab print-outs to study visits) in prior studies.

At study enrollment and 6- and 12-months post-enrollment (and post-intervention start), a member of the study team (trained in phlebotomy) will draw participants' blood for viral load assessment at the APLA Health and Wellness clinic. Alternately, participants can go directly to a Quest lab (where Rise blood samples are sent for processing) to have their blood drawn for the study. Viral load suppression will be defined as <200 copies of virus per milliliter of blood plasma.

If participants wish to go to a Quest lab, we will offer ride assistance, specifically, the Circulation program (e.g., to transport clients from APLA Health & Wellness in Koreatown and Long Beach to Quest Diagnostics blood draw sites). For example, APLA Health in Koreatown is at [name], a half mile away from the closest Quest draw site at [name]. Prior to the appointment, APLA project staff will book a ride through the Circulation portal. The client will meet the APLA staff person at APLA Health's location. The Circulation ride will take the staff person and participant to the Quest draw site, and then back to APLA Health, where the remainder of the session will be completed.

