Potential Covariates will be assessed at baseline, and 6-and 12-months post-baseline. We will assess potential covariates that have previously been related to HIV outcomes. Socio-demographics include race/ethnicity, gender, education level, age, income, employment status, housing status, marital/relationship status, sexual orientation, and incarceration history. Spirituality and Religiosity will be assessed with items from HCSUS. We will use the 6-item Social Support Questionnaire, Revised (alpha = .94). To assess Trauma History, participants will indicate lifetime traumatic experiences on a checklist of 9 traumas from the Posttraumatic Stress Diagnostic Scale. We will assess Usual Care by asking participants to complete a checklist of Standard Clinic Practices for Adherence (e.g., pill boxes). To assess Exposure to Other Adherence Programs, we will ask participants whether they received adherence counseling through medical case management (a Ryan White Care Act program) and extent of exposure (number of sessions, information covered). They will complete a checklist of other Social Services Resources accessed at APLA or elsewhere.

We will assess self-reported adherence using items validated against viral load and pill counts: number of doses missed last week; percentage of prescribed medications taken last month (on a visual analogue scale), and ability to take all medications as prescribed in the past 4 weeks.

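### Nonresponse weights depend on an undefined 'high retention' and a significance test, and the viral-suppression model does not name baseline suppression

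*SAP*

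**What the plan says.** All the missing-data rules are in the first paragraph of the SAP. Inverse-probability weights are to be used on the condition "If we have high retention and find statistically significant differences between respondents and non-respondents at follow-up". The only other rule is "If item non-response is substantial, we will address it through multiple imputations". There is no threshold for high retention, and no rule for participants lost to follow-up when retention is not high.

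The second paragraph gives the models. For Rise's "effects on adherence and viral load, we will use generalized linear mixed models". The adherence model includes the enrollment measurement among its repeated outcomes. The suppression analysis is described as similar logistic regressions "predicting viral load (dichotomized as undetectable vs. detectable) at 6- and 12-months post-enrollment", with no mention of the enrollment value. The covariate rule is "We will use as covariates any socio-demographic, psychosocial, and contextual variables that are associated with the adherence outcome".

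Baseline suppression is available from two sources. Protocol 1A1.2 and Viral Load Assessment 5A1 provide for a study draw at enrollment. Protocol 5A2.4 describes "A blocked 1:1 randomization design with stratification by viral suppression", and 5A2.4 and 5D1 take that stratum from clinic records before baseline.

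**The concern.** Weights for unit non-response matter most when many participants are lost. Read as written, the rule offers them when few are lost and is silent otherwise. If 'high' is a slip for 'low', the threshold is still undefined and the significance test remains. In either case the decision to weight can be made after retention and outcomes are known.

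The suppression model is the one most exposed. In the adherence model a participant who drops out early still contributes an enrollment value. In a model of the 6- and 12-month viral loads alone, a participant with neither value drops out of the analysis, together with what was known about baseline status. Contact also differs by arm: Rise adds 3 core and 2 to 6 booster sessions, 5 to 9 in all (Intervention 5A1), and only Rise participants are told their study viral load results (Viral Load Assessment 5G4.4). Unequal loss is therefore possible, though the documents do not show it.

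**Working it through.** **Inputs.** From the documents: 350 participants, 2 x 175 (Protocol 1A1.2). They give no expected retention or suppression rate, so there is no figure of the plan's own to reproduce on this point. Everything below other than the sample size is assumed.

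**1. What the rule covers.** Retention high and difference significant: weights. Retention high and difference not significant: no weights. Retention not high: no rule.

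**2. Power of the significance condition.** For a 0.3 SD difference between the lost and the retained, two-sided 5% normal test:
- 5% lost (17.5 vs 332.5): SE = sqrt(1/17.5 + 1/332.5) = 0.245; 0.3/0.245 = 1.22; power 23.1%.
- 10% lost (35 vs 315): SE = sqrt(1/35 + 1/315) = 0.178; 0.3/0.178 = 1.68; power 39.1%.

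A missed trigger at 10% loss costs little: the completers' mean shifts by 0.10 x 0.3 = 0.03 SD.

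**3. Bias without baseline suppression.** Assume no true effect, 60% suppressed at baseline, and follow-up suppression of 85% (suppressed at baseline) or 40% (not). True suppression is 0.6 x 0.85 + 0.4 x 0.40 = 67% in both arms. With retention r1 (suppressed) and r0 (unsuppressed), the expected observed proportion in an arm is

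(0.6 r1 x 0.85 + 0.4 r0 x 0.40) / (0.6 r1 + 0.4 r0).

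For 15% vs 30% loss with strong dependence on baseline:
- Rise (loss 10% / 22.5%): (0.459 + 0.124)/0.85 = 0.686.
- Control (loss 15% / 52.5%): (0.4335 + 0.076)/0.70 = 0.728.
- Difference: -4.2 points.

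| Loss, suppressed / unsuppressed at baseline: Rise | Control | Overall loss | Bias, points |
|---|---|---|---|
| same pattern | same pattern | equal | 0 |
| 3.3% / 7.5% | 6.7% / 15% | 5% vs 10% | -0.5 |
| 6.7% / 15% | 10% / 35% | 10% vs 20% | -2.4 |
| 10% / 22.5% | 20% / 45% | 15% vs 30% | -2.3 |
| 10% / 22.5% | 15% / 52.5% | 15% vs 30% | -4.2 |

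In the fourth row the relative risk of loss is the same in both arms, but every loss rate is doubled in control. The ratio r0/r1 is then 0.775/0.90 = 0.86 in Rise and 0.55/0.80 = 0.69 in control, and the bias follows that ratio.

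**4. The planned mixed model.** A two-visit random-intercept logistic model was simulated under the last row (random-effect SD 1.5, 1,000 runs, Monte Carlo SE about 0.15). The 12-month bias without baseline suppression was -4.2 points (SD 4.8) if all the lost miss both viral loads, -2.2 if half do, and -0.8 if none do. With baseline suppression it was 0.0 to +0.1. A separate calculation placed baseline-dependent loss in Rise and even loss in control, with all the lost missing both values. It gave the opposite sign: +1.0 to +1.9 points at about 10% loss and +3.8 to +7.0 at about 30%, and 0.0 with baseline in the model.

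**5. What remains after adjustment.**
- The zero in step 4 follows from the assumption that loss depends only on arm and on the baseline measure used.
- If non-responders are d points less suppressed within baseline status, the residual at 15% vs 30% loss is (0.15 - 0.30) x d: -1.5 points at d = 10 and -3.0 at d = 20.
- If the model holds only the record-based stratum, and it agrees with enrollment status in 95%, 90% or 80% of participants, the residual in the last row is -1.0, -1.8 or -3.0 points.

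**The case against.** The SAP does not forbid weights at low retention; it is silent. A reader might infer that the plan refuses weights exactly when they are needed, but the text supports only the absence of a rule, and 'high' may be a slip.

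The first SAP paragraph also says that covariates related to the primary study variables will be treated as confounders. That sentence, or the word 'similar' in the suppression sentence, might admit baseline viral load. The survey covariate list in Protocol 5C5.2, introduced by "We will assess potential covariates that have previously been related to HIV outcomes", contains no viral load, but it describes only the survey component, so this proves little. The objection stands as far as it goes: inclusion is possible, but not guaranteed.

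The planned mixed models give some protection under missing at random to participants with one of the two viral loads. The bi-monthly downloads, visit payments, rides and home device pick-up are not described as arm-specific, so loss could be small or balanced.

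Clinic records might fill gaps: "After the 12-month follow-up, we will extract past 2-year viral load, CD4 counts, ART prescriptions, clinic visits, and associated dates". A reader might fault the SAP for having no rule on using record or photographed viral loads in place of a missed draw. The photo route is a COVID-19 provision and the SAP is dated October 2017, so the 2017 text could not have foreseen it. Any substitution rule is a matter for a later amendment.

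**Conclusion.** The concern holds in a limited form and the plan should be changed. The trigger for weights is undefined and gated on a weak test, heavier loss has no unit non-response rule, and the suppression model does not commit to baseline suppression. Under the assumptions above the bias runs from 0 to about -4 points on the suppression difference. At its largest in those scenarios it is still below one SD of the estimate (4.8 points in the mixed model).

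Size and sign both come from assumed loss. The documents do not support inferring that the trial's result is biased, or in which direction: the sign depends on which arm loses more and, at equal overall loss, on which arm loses more of its unsuppressed participants. Nor do they support the claim that adding baseline suppression settles the matter, since it removes only the bias from loss which that variable explains. If 'similar' means a separate regression at each visit, missing one visit has the same effect at that visit as missing both.

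**What to change.** 1. Delete the retention condition and the significance condition. Name one unit non-response method, either weights or multiple imputation using arm, baseline suppression and baseline MEMS adherence, and apply it at any retention level.
2. Include in the suppression model both the randomisation stratum (from clinic records) and suppression at the enrollment draw. They are different measurements and one does not stand in for the other.
3. Report loss by arm, including the number with neither follow-up viral load.
4. Add a sensitivity analysis for departures from missing at random, for example non-responders 0 to 20 points less suppressed within baseline status, allowed to differ by arm. Counting missing as not suppressed is no substitute: in the no-effect scenario with 15% vs 30% loss it gives 0.583 - 0.5095 = +7.35 points in favour of Rise.

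The cost is SAP wording and modest analysis time; both baseline measures are already in the protocol. In one-visit simulations of the same scenario, standardising for baseline suppression slightly narrowed the spread of the estimate (SD 5.4 vs 5.6 points unadjusted) and weights slightly widened it (5.9).
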